## 1. **PROTOCOL AND AMENDMENTS**

- SYNT001-103 Protocol Version 1, 18 January 2017
- SYNT001-103 Protocol Amendment 1.1, 21 March 2017
- SYNT001-103 Protocol Amendment 1.1 SOC, 21 March 2017
- SYNT001-103 Protocol Amendment 2.0, 12 April 2017
- SYNT001-103 Protocol Amendment 2.0 SOC, 12 April 2017
- SYNT001-103 Administrative Letter 1.0, 10 May 2017
- SYNT001-103 Administrative Letter 2.0, 11 August 2017
- SYNT001-103 Administrative Letter 3.0, 21 September 2017
- SYNT001-103 Protocol Amendment 3.0, 10 October 2017
- SYNT001-103 Protocol Amendment 3.0 SOC, 10 October 2017
- SYNT001-103 Administrative Letter 4.0, 02 March 2018
- SYNT001-103 Protocol Amendment 4.0, 08 June 2018
- SYNT001-103 Protocol Amendment 4.0 SOC, 08 June 2018
- SYNT001-103 Protocol Amendment 5.0, 18 September 2018
- SYNT001-103 Protocol Amendment 5.0 SOC, 18 September 2018

## PROCEDURES IN CASE OF EMERGENCY

### Serious Adverse Events

Any death, serious adverse event (SAE)\* occurring in a subject while receiving study drug or within 7 days of receiving study drug, even though the event may not appear to be study drug related, must be promptly reported (within 24 hours) by telephone or electronic communication to the sponsor (or designee).

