#### 11.3.1 Serious Adverse Events

*(Notify Medpace Safety within 24 hours; document on eCRF)*

The SAE definition and reporting requirements are in accordance with Title 21 Part Code of Federal Regulations (CFR) 312.32 and the Guidance for Industry and Investigators Safety Reporting Requirements for Investigational New Drug (INDs) and Bioavailability /Bioequivalence Studies.

SAE: An AE is considered "serious" if, in the view of either the Investigator or sponsor, it results in any of the following outcomes:

- **Death:** This includes any death that occurs while the subject is "on study" as well as any death that occurs within 28 days after study drug administration.

**Note:** Death is an outcome of an AE, and not an AE. The event(s) that caused death (e.g., illness, accident) is the SAE. Death due to any other cause(s) must also be reported as an outcome of the reportable SAE.

- **Life-threatening adverse drug event:** An AE or suspected adverse reaction is considered "life threatening" if, in the view of either the Investigator or sponsor, its occurrence places the patient or subject at immediate risk of death. It does not include an AE or suspected adverse reaction that, had it occurred in a more severe form, might have caused death.

- **Inpatient hospitalization or prolongation of existing hospitalization:**

In the absence of an AE, the Investigator should not report hospitalization or prolongation of hospitalization. This is the case in the following situations:

- Hospitalization or prolongation of hospitalization is needed for a procedure required by the protocol
- Hospitalization or prolongation of hospitalization is part of routine procedure followed by study center

- Hospitalization for survey visits or annual physicals
- Hospitalization for observation with release within 24 hours

In addition, a hospitalization planned before the start of the study for a pre-existing condition, which has not worsened, does not count as an SAE.

- **Persistent or significant incapacity or substantial disruption of the ability to conduct normal life functions**
- **Congenital anomaly/birth defect**
- **Important medical event:** An event that may not result in death, be life threatening, or require hospitalization may be considered an SAE when, based upon appropriate medical judgment, it may jeopardize the subject and may require medical or surgical intervention to prevent one of the outcomes listed in this definition.

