**11.3.9.2 Time Frame for Reporting**

Any death, SAE, pregnancy, or unexpected (and severe) AE experienced by the subject after informed consent or within 28 days of receiving study drug, regardless of relationship to study drug, or any death that occurs more than 28 days after receiving study drug, and is believed to be study drug related, must be promptly reported (within 24 hours of the Investigator becoming aware of the event) by telephone or electronic transmission to the sponsor (or designee).

Contact information for **SAE** reporting:

Medpace Clinical Safety  
Medpace SAE hotline:  
Telephone: PPD [redacted] dial P or PPD [redacted] dial PPD  
Facsimile: PPD [redacted] D or PPD [redacted]  
e-mail PPD [redacted]

Additionally, the Investigator will be able to contact the **Medical Monitor**:

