### 11.3.9.3 Information to be Provided by the Investigator

SAEs must be recorded on the SAE form in the EDC system. This requirement includes all SAEs that occur after informed consent and through 28 days after study drug dosing, and in addition, any SAE that are assessed as related to study treatment by the Investigator, even if the SAE occurs more than 28 days after study drug dosing.

The minimum information required for SAE reporting includes identity of Investigator, site number, subject number, an event description, SAE term(s), onset date, the reason why the event is serious (i.e., the seriousness criteria) and the Investigator's assessment of the relationship of the event to study treatment. Additional SAE information including medications or other therapeutic measures used to treat the event, action taken with the study treatment due to the event, and the outcome/resolution of the event will be recorded. Paper forms for reporting SAEs will be provided to the study sites as back-up in case the EDC system is not accessible.

In all cases, the Investigator should continue to monitor the clinical situation and report all material facts relating to the progression or outcome of the SAE. Furthermore, the Investigator may be required to provide supplementary information as requested by Syntimmune or designee.

When reporting an SAE, the following additional points should be noted:

- When the diagnosis of an SAE is known or suspected, the Investigator should report the diagnosis or syndrome as the primary SAE term, rather than as signs or symptoms. Signs and symptoms may then be described in the event description. For example, dyspnea should not be used as an SAE term if the diagnosis, which caused the dyspnea, is known to be malignant pleural effusion.
- Death should not be reported as an SAE, but as an outcome of a specific SAE, unless the event preceding the death is unknown. In the exceptional case where the events leading to death are unknown, then death may be used as an event term. If an autopsy was performed, the autopsy report should be provided.
- While most hospitalizations necessitate reporting of an SAE, some hospitalizations do not require SAE reporting, as follows:
  - Elective or previously scheduled surgery, e.g., a previously scheduled ventral hernia repair
  - Procedures for pre-existing conditions that have not worsened after initiation of treatment
  - Pre-specified study hospitalizations for observation

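### The emergency page sets a 7-day window for 24-hour SAE reporting where Section 11.3.9.2 sets consent to 28 days, so a site relying on the page can give late or no notice of later SAEs

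*Protocol*

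**What the plan says.** Procedures in Case of Emergency, at the front of the protocol, states that any death or SAE "occurring in a subject while receiving study drug or within 7 days of receiving study drug" must reach the sponsor or its designee within 24 hours, whether or not it looks drug related. The protocol file carries this page twice, with the same sentence each time. The page's one cross-reference is to Section 11.3.1, for more on the SAE criteria.

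Section 11.3.9.2 sets the same 24-hour deadline, running from the investigator's awareness, for deaths, SAEs, pregnancies and unexpected severe AEs "experienced by the subject after informed consent or within 28 days of receiving study drug, regardless of relationship to study drug". Beyond 28 days it extends the duty to deaths believed to be drug related.

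Section 11.3.9.3 governs the SAE form in the data capture system. It covers "all SAEs that occur after informed consent and through 28 days after study drug dosing", and also later SAEs that the investigator assesses as related.

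The synopsis, Table 1 and Sections 6.10 and 11.2 collect AEs over the same period, from consent to 28 days after dosing. Section 11.3.1 gives a 28-day figure for deaths only: "any death that occurs within 28 days after study drug administration".

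**The concern.** Two places in one protocol give different windows for the same duty, and the shorter one is on the page written for use when an event happens. A site that works from that page would have no instruction to call in an SAE arising in screening or more than 7 days after the last infusion, and the page does not send it to the section that says otherwise.

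Prompt notice does specific work in this study. A related Grade 4 event suspends dosing in all enrolled subjects (Section 8.4.2). Two subjects in a cohort with related, clinically significant Grade 3 events, at any time, halt dosing in that cohort and end escalation (Section 8.4.1). The DEC reviews drug-related SAEs throughout the study (Section 14.5) and decides on the next cohort from data through Day 42 (Section 11.5). The 15-day regulatory clock starts at the sponsor's initial notification (Section 11.3.9.1), so late notice from a site moves the whole sequence back.

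**Working it through.** The protocol gives no figure of its own to reproduce. The check compares the windows and counts days.

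**Inputs**
- Dosing on Days 0, 7, 14, 21 and 28 (Section 9.3).
- Last visit on Day 56, 28 days after the last dose (Section 4.3).
- Screening from Day -14 to Day -1 (Section 7.1).
- DEC review of data through Day 42 (Section 11.5).
- Within a cohort, subject 2 starts at least 24 hours after subject 1; the other six wait for 7-day data on both (Section 9.2).

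**The two windows for a subject given all five doses**

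| Period | Emergency page | Section 11.3.9.2 |
|---|---|---|
| Consent to first dose (up to 14 days) | not covered | covered |
| Day 0 to Day 35 | covered | covered |
| Day 36 to Day 56 | not covered | covered |

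1. The emergency page's window ends on Day 28 + 7 = Day 35.
2. The Section 11.3.9.2 window ends on Day 28 + 28 = Day 56.
3. The difference is 56 - 35 = 21 days (Days 36 to 56). As a share of the post-dose follow-up, 21/28 = 75%.
4. Doses are 7 days apart, so a subject on schedule is never more than 7 days from a dose before Day 35. The windows agree from the first dose to that point.
5. A subject who stops early is followed for 28 days after the last dose (Sections 5.1 and 8.3). The windows part on days 8 to 28 after that dose, again 28 - 7 = 21 days.

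**Overlap with the DEC review.** Days 36 to 42 are 42 - 35 = 7 days. That is 7 of the 14 days from Day 29 to Day 42 (50%), or 7 of the 43 days from Day 0 to Day 42 (16%). The second share is the fairer one, because the review takes in the whole period.

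**Overlap with dosing of other subjects.** Count in subject 1's study days. Subject 2 starts no earlier than Day 1. Seven-day data on both are available no earlier than Day 1 + 7 = Day 8, so the other six start no earlier than about Day 8. Their fifth dose falls no earlier than about Day 8 + 28 = Day 36. When subject 1 enters the uncovered period, others in the cohort can still be receiving infusions, so late notice could delay a stop.

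**The case against.** The strongest reply is that this is a drafting inconsistency with little consequence, because Section 11 already covers everything. Much of that stands.

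- A reader might infer that the two rules cannot both be followed. They can: the 28-day window contains the 7-day one, and the page does not forbid later reporting. What is true is that a site following the page alone can breach Section 11.3.9.2.
- A reader might infer that the safety results are biased downwards. The documents do not support that. The page governs expedited notice, not data capture. The synopsis and Sections 6.10, 11.2 and 11.3.9.3 require these events to be recorded, AE assessment is scheduled at Days 42 and 56 (Sections 7.15 and 7.16), and monitors verify the case report forms against source (Section 13).
- A reader might infer that a cohort would escalate on incomplete data. The DEC reviews all safety data through Day 42, not just events that were telephoned in. What remains is late awareness of an event between visits.
- A reader might call Days 36 to 56 an infection-risk window. Section 9.6.2 expects IgG to fall by up to 70% to 80% after multiple doses and to recover within 4 weeks, but the multiple-dose recovery time comes from non-human primates and no infection rate by day is given.
- The page does refer to Section 11.3.1, which opens with a 24-hour notification instruction and no 7-day limit. That softens the conflict without resolving it, since Section 11.3.1 gives no reporting window for SAEs in general.

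**Conclusion.** The emergency page is wrong as written and must be reconciled with Sections 11.3.9.2 and 11.3.9.3. A site relying on it could give late or no 24-hour notice of SAEs over 21 of the 28 days after the last dose and over up to 14 days of screening. The consequence is delayed sponsor and DEC awareness for the stopping rules, the Day 42 review and expedited reporting. Lost data or bias is not shown.

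The conclusion rests on three assumptions: that Section 11.3.9.2 means consent through 28 days after the last dose, as the AE collection period does; that dosing keeps to the weekly schedule; and that some sites act on the front page without turning to Section 11.3.9.2. The documents do not show how often the last would happen or how many SAEs would be affected, so the size is given in days of exposure to the error and not in events.

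**What to change.** In both copies of the emergency page, replace the 7-day sentence with the actual text of Section 11.3.9.2. Keep its provisions for pregnancy, unexpected severe AEs and related deaths after 28 days. Add a cross-reference to Section 11.3.9.2 for timing and to Section 11.3.9.3 for later related SAEs. A free paraphrase should be avoided: Section 11.3.9.2 extends 24-hour reporting past 28 days for related deaths only, while the extension to later related SAEs belongs to the SAE form in Section 11.3.9.3. Merging the two would create a third version of the rule.

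Send the corrected page to sites now. Have monitors check, for subjects already enrolled, that SAEs with onset before the first dose or more than 7 days after the most recent dose were reported within 24 hours of awareness.

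The cost is one sentence and its cross-references in the next amendment, a site letter and a short monitoring check. No new data are collected, because Section 11 already requires these events.

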### SAE CRITERIA

\* A serious adverse event (SAE) is any untoward medical occurrence that at any dose results in any of the following outcomes, regardless of relationship to study drug (see [Section 11.3.1](#), Serious Adverse Events for additional information):

- Death
- Life-threatening adverse drug event
- Inpatient hospitalization or prolongation of existing hospitalization
- A persistent or significant disability/ incapacity
- A congenital anomaly/birth defect
- An important medical event that may jeopardize the subject and may require medical or surgical intervention to prevent one of the outcomes listed above.

**1 SYNOPSIS**

Study title	A Phase 1b, Multicenter, Open-Label, Safety, Tolerability, and Activity Study of SYNT001 in Subjects with Chronic Pemphigus (Vulgaris or Foliaceus)
Protocol number	SYNT001-103
Number of study centers	Approximately 10 (US)
Clinical phase	Phase 1b
Study background	
SYNT001, a humanized, affinity-matured IgG4-kappa monoclonal antibody (mAb), blocks IgG and IgG immune complex (IC) interactions with the neonatal Fc receptor (FcRn) and thereby the major functions of FcRn in protecting IgG and IgG immune complexes from degradation and their role in downstream signaling events. Specific and high affinity blockade of FcRn with SYNT001 has been shown to increase the catabolism of IgG and IgG IC in healthy volunteers. This predicts that SYNT001 will also accelerate degradation of endogenous circulating IgG autoantibodies and IgG-antigen IC specifically involved in the pathogenesis of autoimmunity. Blocking FcRn interactions with IgG containing immune complexes further predicts that SYNT001 will have consequences for innate and adaptive cellular immunity. In the first instance, blocking multimeric IgG IC interactions with FcRn within antigen presenting cells will result in inhibition of IC-stimulated inflammatory cytokine production and release by these cells. In addition, as FcRn determines the intracellular itinerary of IgG immune complexes within and among compartments important in cellular immunity, it is further anticipated that SYNT001 will block antigen processing and presentation of antigens contained within IC that otherwise lead to CD8+ and CD4+ T cell activation. Thus, SYNT001 will specifically target immune functions associated with IgG and IC that are involved in many autoimmune conditions and dismantle their ability to cause disease.
 
SYNT001 targets mechanisms contributing to pathology in a variety of IgG-mediated autoimmune disorders, including warm antibody autoimmune hemolytic anemia (WAIHA), pemphigus, and chronic inflammatory demyelinating polyneuropathy (CIDP).
 
While current treatments for certain autoimmune disorders including chronic steroids, immunosuppressants, intravenous immunoglobulin (IVIG), plasmapheresis, and anti-CD20 monoclonal antibodies (mAbs), such as rituximab, can be effective, they are frequently associated with significant adverse effects, and delayed or non-durable responses.
 
Pemphigus is a rare group of blistering autoimmune diseases that affect the skin and mucous membranes. Autoantibodies are thought to play an important

	
pathogenic role in the mucosal and cutaneous manifestations in patients with pemphigus. Administration of SYNT001, leading to a significant decrease in total IgG, and thereby a corresponding decrease in the level of the pathogenic autoantibodies as well as the ICs to which they are associated, should lead to a decrease in the mucosal and cutaneous manifestations in subjects with pemphigus. Moreover, the ability of SYNT001 to reduce circulating immune complexes (CICs) and the associated innate and adaptive immune responses may allow for further sustained disease modification.

Study rationale
	
This study is being conducted to further evaluate the safety, tolerability, pharmacokinetics (PK), pharmacodynamics (PD) and immunogenicity of intravenous (IV) SYNT001 as well as its effects on pemphigus disease activity markers.

Study objectives
	
Primary objective
 
 
• To evaluate the safety and tolerability of 5 once-weekly IV infusions of SYNT001 at different dose levels in subjects with chronic pemphigus (vulgaris or foliaceus)
 
 
Secondary objectives
 
 
• To determine the PK of SYNT001 following 5 once-weekly 1-hour IV infusions at different dose levels
 
• To assess the effect of 5 once-weekly doses of SYNT001 at different dose levels on the following PD biomarkers: 
 
○ Immunoglobulins: IgG, IgG subtypes (IgG1-4), IgA, IgM
 
○ Albumin
 
 
 
• To assess the effect of 5 once-weekly doses of SYNT001 at different dose levels on the following disease activity markers: 
 
○ Serum anti-desmoglein (Dsg) (1 and 3) antibody levels
 
○ Pemphigus Disease Area Index (PDAI)
 
 
 
• To assess immunogenicity (anti-SYNT001 antibodies)
 
 
Exploratory objectives
 
 
• To assess the effect of 5 once-weekly doses of SYNT001 at different dose levels on the following biomarkers, including: 
 
○ Serum anti-epithelial cell antibody (AECA) levels by indirect immunofluorescence
 
○ Circulating immune complexes (CIC)
 
○ Complement component 3 (C3)
 
○ Exploratory biomarkers (FCGR2A (single nucleotide polymorphism-SNP), RNAseq, urine IgG)
 
 
 

	
 
○ Immune phenotyping by flow cytometry for CD3+CD4+ T, CD3+CD8+ T, monocytes, NK cells and B cells
 
○ SYNT001 levels in skin biopsies (optional)
 
● To characterize corticosteroid use during the study
 
									
Study design	Phase 1b, multicenter, open-label, safety, tolerability, and activity study									
Methodology	
Two cohorts of 8 eligible subjects each will receive 5 once-weekly 60-minute infusions of SYNT001 in planned doses of 10 mg/kg or 30 mg/kg. Based on review of safety, PD, and clinical outcomes of these 2 cohorts, a third cohort of up to 8 subjects may be treated at another dose, with a maximum dose of 45 mg/kg, but may also be lower than 10 mg/kg or between 10 and 30 mg/kg, inclusive.
 
  
 Cohort	No. of subjects	Dose	
   
 1	8	SYNT001 10 mg/kg	
 
 2	8	SYNT001 30 mg/kg	
  
 
Cohorts will be dosed sequentially beginning with Cohort 1. The first 2 subjects will be dosed at least 24 hours apart. A review of the 24-hour safety data for the first subject will be performed to ensure that there are no overt safety concerns before dosing the second subject. A review of the 7-day safety data for the first 2 subjects will be performed prior to dosing the remaining 6 subjects in the cohort. This evaluation will include a review of AE/SAE reports, vital sign assessments, physical examinations, ECGs, and clinical laboratory testing. The seriousness, severity, and relatedness of AEs/SAEs will also be considered in the safety evaluation. Safety data will be reviewed on a continuous basis throughout the study. All safety data and any available and relevant PD data through Day 42 (2 weeks after the last subject's last dose in Cohort 1) will be reviewed by a dose escalation committee before Cohort 2 is initiated. Escalation to Cohort 2 will proceed if there are no concerning safety signals and the review of available and relevant PD data supports advancing to a higher dose. The dose for Cohort 2 will be finalized after review of the safety and PD data, but will not exceed 30 mg/kg. Cohort 2 and Cohort 3, if added, will be dosed per the same schedule as Cohort 1.
 
On days where study drug is administered, vital sign and pulse oximetry measurements will be collected immediately prior to the infusion; 15, 30, and 45 minutes after the start of the infusion; at completion of the infusion; and 30 minutes, 1 hour and 2 hours following completion of the infusion.
 
On Days 0 and 28, PK blood samples will be collected prior to infusion start and then over the subsequent 48 hours. Subjects will remain at the clinic through the 6-hour PK sample collection and will return to the clinic for the 24- and 48-hour collections. Additional samples will be collected on Days 5 and 33.
	Cohort	No. of subjects	Dose	1	8	SYNT001 10 mg/kg	2	8	SYNT001 30 mg/kg
Cohort	No. of subjects	Dose								
1	8	SYNT001 10 mg/kg								
2	8	SYNT001 30 mg/kg								

	
On Day 0 photographs will be taken of active lesions. Follow-up photographs will be taken of the same areas on Days 33 and 56. If a subject begins a steroid taper, additional photographs will be taken at the clinic visit during which the decision to begin the taper is made.
 
Subsequent visits will occur on Days 1, 2, 5, 7, 12, 14, 19, 21, 28, 29, 30, 33, and 42 for safety assessments, study drug dosing, sample collections, and other study procedures.
 
Subjects also will return to the clinic on Day 56 (28 days after receiving their last dose of study drug) for an End-of-Study/Follow-Up visit.
 
See Table 1 for a schedule of all study events. To assess safety and tolerability, subjects will undergo physical examinations (PEs; including weight), vital sign measurements, clinical (safety) laboratory tests, adverse event (AE) assessments, concomitant medication assessments, and electrocardiograms (ECG).

Number of subjects
	
Approximately 16; two cohorts of 8 subjects each. An additional cohort of up to 8 subjects may be enrolled. Subjects who withdraw for any reason other than an AE and who do not receive study drug or have only received one dose of study drug may be replaced, up to one subject per cohort. The maximum number of subjects who may be enrolled in this study is 27 (24 + up to 3 replacements, as necessary). Within each dosing cohort, no more than 3 subjects with pemphigus foliaceus may be enrolled.


Diagnosis and main entry criteria
	
Inclusion criteria:
 
Subjects must meet the following criteria to be included:
 
 
1. Willing and able to read, understand and sign an informed consent form;
 
2. Male or female <math>\geq</math> 18 years of age at the time of screening;
 
3. Documented diagnosis of pemphigus vulgaris or foliaceus based on all 3 of the following criteria:             
 
a. Documented clinical history consistent with pemphigus vulgaris or foliaceus (clinical presentation defined as mucosal and/ or skin lesions);
 
b. Presence of Anti-Dsg 1 or 3 antibodies above the upper limit of normal;
 
c. History of at least one positive tissue-based test (e.g., biopsy, direct immunofluorescence [DIF])
 
 
 
4. Active disease: Lesions lasting <math>></math> 2 weeks, and 3 active lesions in skin or mucosa or 2 active lesions with at least one being a skin lesion <math>></math> 1 cm diameter:             
 
a. If treated with rituximab or other anti-CD20 antibodies, last dose <math>></math> 12 months prior to screening;
 
 
 

	
 
b. If being treated with other immunosuppressants (i.e., azathioprine, mycophenolate mofetil or cyclosporine), must be on stable dose (< 10% change in dose) for 6 weeks prior to screening;
 
c. If being treated with corticosteroids, must be <math>\leq</math> 1mg/kg/day and stable (< 10% change in dose) for 2 weeks prior to screening;
 
d. Allowed topical therapies for pemphigus lesions upon entering the study include petroleum jelly or Aquaphor® for the skin or chlorhexidine for the mouth
 
 
 
5. Body mass index (BMI) 18.5 – 35.0 kg/m^2;
 
6. Has a negative urine pregnancy test (for women of childbearing potential) documented prior to the first dose of study drug;
 
7. Females of childbearing potential must agree to be abstinent or else use any two of the following medically acceptable forms of contraception (<1% per year failure rate) from the Screening Period through 60 days after the final study dose: oral contraceptive, condom with or without spermicidal jelly, diaphragm or cervical cap with spermicidal jelly, or intra-uterine device (IUD). A female whose male partner has had a vasectomy must agree to use one additional form of medically acceptable contraception.
 
8. Females of non-childbearing potential, defined as surgically sterile (status post hysterectomy, bilateral oophorectomy, or bilateral tubal ligation) or post-menopausal for at least 12 months do not require contraception during the study.
 
9. Males with female partners of childbearing potential, including males who are surgically sterile (post vasectomy), must agree to be abstinent or else use a medically acceptable form of contraception from the screening period through 60 days after the final study dose.
 

	
Exclusion criteria:
 
Subjects meeting any of the following criteria are to be excluded:
 
 
1. Subject unable or unwilling to comply with the protocol;
 
2. Active non-hematologic malignancy or history of non-hematologic malignancy in the 3 years prior to screening (exclusive of non-melanoma skin cancer and cervical cancer in situ);
 
3. Positive for HIV or hepatitis C antibody;
 
4. Positive for hepatitis B surface antigen;
 
5. Active infection or history of recurrent infections;
 
6. IVIG use within 60 days of screening;
 
7. Received any cytotoxic (other than azathioprine) or mAb therapy in the 3 months prior to screening;
 
8. Any exposure to an investigational drug or device within the 30 days prior to screening
 
9. Plasmapheresis or immunoadsorption within 60 days of screening
 

	
10. Cellular therapy at any time prior to screening
 
11. Use of any immunosuppressive drugs apart from corticosteroids, azathioprine, mycophenolate mofetil, or cyclosporine within 3 months of screening
 
12. Serum total IgG < 600 mg/dL;
 
13. Subject has any current medical condition that, in the opinion of the Investigator, may compromise their safety or compliance, preclude successful conduct of the study, or interfere with interpretation of the results (e.g., a significant pre-existing illness or other major comorbidity that the Investigator considers may confound the interpretation of the study results);
 
14. Any vaccination within 2 weeks of screening

Study drug, dosage, and administration	
SYNT001
 
Doses: 10 mg/kg and 30 mg/kg. A third cohort of up to 8 subjects may be treated at another dose, with a maximum dose of 45 mg/kg, but may also be lower than 10 mg/kg or between 10 and 30 mg/kg, inclusive.
 
SYNT001 is provided as a liquid at a nominal concentration of 50 mg/mL. SYNT001 is diluted in Dextrose 5% in Water (D5W) to prepare the solution for infusion.
 
Route of administration: IV in 250 mL over 1 hour

Control, dose, and route of administration	
Not applicable

Duration of subject participation and duration of study	
Up to 70 days (10 weeks): Screening of up to 2 weeks (14 days); dosing period of 4 weeks (28 days); and 4 weeks (28 days) of follow-up


Prohibited Concomitant treatments
	
All treatments a subject receives within 14 days prior to enrollment through the end of the study (Day 56) will be documented. Concomitant medication and treatment for co-existing conditions, including those for pemphigus, are permitted if not excluded below. Topical antibiotics are permitted to treat active infections that occur on study. Topical or systemic treatments for oral candidiasis are permitted. Topical lidocaine for transient pain relief is acceptable as needed. Significant increases in anti-pemphigus medications may result in subjects being discontinued from the study. Concomitant treatment that is medically indicated for any AEs the subject experiences during the study are permitted.
 
Use of the following medications will not be permitted during the study unless otherwise specified:
 
 
• Rituximab or other anti-CD20 antibody
 
• Monoclonal antibodies other than study drug
 
• Any immunosuppressive drugs apart from corticosteroids, azathioprine, mycophenolate mofetil, or cyclosporine
 
• Topical steroids
 
• Any dietary herbal supplements
 
• Any investigational drug or device
 
• Any vaccinations
 
 
If over a period of at least two weeks on study drug, a subject on corticosteroids shows the absence of new lesions and significant healing of lesions that existed at study baseline, a slow corticosteroid taper may be started as per the following suggested schedule
 
 
• If on > 30 mg of prednisone per day, decrease by 10 mg every two weeks until a dose of 30 mg per day then decrease by 5 mg every two weeks
 
• If on < 30 mg of prednisone per day, decrease by 5 mg every two weeks
 


Safety assessments
	
Safety assessments include AEs, serious adverse events (SAEs), PEs, vital sign measurements, clinical safety laboratory evaluations, ECGs, and reasons for treatment discontinuations due to toxicity. Safety assessments will be performed at specified time points and prior to discharge from the clinic. Vital sign measurements, including blood pressure, pulse rate, respiratory rate, and temperature will be monitored throughout the study. Pulse oximetry will be monitored during the study drug infusion and for 2 hours following the end of the infusion.
 
The National Cancer Institute Common Terminology Criteria for Adverse Events (NCI CTCAE; Version 4.03) will be used for grading clinical and laboratory AEs.

	
The AE reporting period for a subject enrolled in the study begins when the subject provides informed consent and is continued for 28 days after the last dose of study drug. All AEs that occur in the enrolled subjects during the AE reporting period must be recorded, regardless of the relationship of the AE to study drug. Any known untoward event that occurs beyond the AE reporting period that the Investigator assesses as related to study drug should also be recorded.

Dose-escalation rules	
Dose-limiting toxicity (DLT) will be defined generally as clinically significant, severe (Grade 3) AEs occurring in <math>\geq 2</math> subjects that are determined to be clinically significant and considered related to study drug.
 
If 2 or more subjects at any time in any cohort (8 total subjects per cohort) have Grade 3 AEs that are determined to be clinically significant and considered to be related to study drug, dosing will be halted within that cohort and no further dose-escalation will occur. If the dose-escalation stopping rule is met in Cohort 1 (10 mg/kg) all safety data and all available pharmacodynamics data will be reviewed and a cohort may be added at a dose at least 50% lower than the 10 mg/kg dose. If the stopping rule is not met after Cohort 1 (10 mg/kg), dose-escalation may proceed up to a maximum of 30 mg/kg. If the dose-escalation stopping rule is met in Cohort 2, all safety data and all available pharmacodynamics data will be reviewed and a cohort may be added at a dose at least 30% lower than the Cohort 2 dose. If the stopping rule is not met after Cohort 2, dose-escalation may proceed up to a maximum of 45 mg/kg; however, this cohort may also receive a dose equal to or less than 30 mg/kg based on evaluation of all safety and pharmacodynamic data.

Study stopping rule	
If any subject experiences a life-threatening AE (Grade 4) that is considered to be related to study drug, any further dosing in all enrolled subjects will be suspended until the DEC has evaluated the event and determined the next appropriate course of action. At any time during the study, the study may be discontinued if the DEC determines that further drug exposure would pose an undue risk to subjects.

Individual stopping rule	
Dosing for any individual subject will be discontinued (i.e., further treatment with the study drug will not be given) if the subject experiences any study drug-related SAE or any study drug-related non-SAE adverse event that, in the judgement of the Investigator and Medical Monitor, suggest that it could be unsafe to administer further study drug to that subject. Additionally, a subject may be discontinued from further treatment with study drug, at the discretion of the Investigator with consultation with the Medical Monitor, if they require a

	significant increase in dose(s) of anti-pemphigus medication(s) for the management of pemphigus.
Pharmacokinetics	
The PK of SYNT001 will be evaluated following the first and last (fifth) doses of SYNT001.
 
Starting on Days 0 and 28, serum samples will be collected just prior to the start of study drug infusion (pre-dose), at 5 minutes and 2, 4, 6, 24, and 48 hours after the end-of-study drug infusion. Additional samples will be collected on Days 5 and 33.
 
Study drug concentration will be used to calculate the following PK parameters: <math>t_{1/2}</math>, <math>C_{max}</math>, <math>T_{max}</math>, <math>AUC_{0-24}</math>, and <math>AUC_{0-\infty}</math>.

Pharmacodynamics/ Activity	
PD samples will be collected for analysis of IgG (serial assessment of IgG levels to identify <math>C_{min}</math>, <math>T_{min}</math>); IgG1-4 subtype levels; IgA levels; IgM levels; albumin levels; anti-Dsg (1 and 3) antibody levels; serum AECA by direct immunofluorescence; CIC; C3; exploratory biomarkers (FCGR2A SNP, RNAseq, urine IgG, <math>CD3^+CD4^+</math> T, <math>CD3^+CD8^+</math> T, monocytes, NK cells and B cells).

Immunogenicity	
Up to 4 samples will be collected for immunogenicity analyses. Samples will be collected on Days 0 (pre-dose), 14, 28, and 56.

Skin biopsy	
Optional skin biopsy samples will be collected on Day 0 pre-dose and on Days 1, 2, 14, 33 and 56 to analyze SYNT001 levels.

Photography	
Photographs of active lesions will be taken at Day 0. Follow-up photographs of the same areas will be taken on Days 33 and 56. Subjects who begin a steroid taper will have additional photographs taken at the clinic visit during which the decision to begin the taper is made.

Statistical methods	
Sample size consideration
 
Formal sample size calculations were not performed. The number of subjects was chosen based on feasibility and was considered sufficient to meet the study objectives.
 
Data presentations/Descriptive statistics
 
Three populations will be employed in the analysis of study data.
 
 
• The intent-to-treat (ITT) population will consist of all subjects who have received at least one dose of study drug. All safety analyses will be performed on the ITT population.
 
• The PK population will consist of all subjects who receive at least one dose of study drug and have sufficient post-dose blood samples to obtain PK parameters.
 

